8.1 Definitions

Unanticipated Problems Involving Risk to Subjects or Others

Any incident, experience, or outcome that meets all of the following criteria:

- Unexpected in nature, severity, or frequency (i.e., not described in study-related documents such as the IRB-approved protocol or consent form, the investigators brochure, etc)

CONFIDENTIAL

This material is the property of the NYU School of Medicine and Langone Health. Do not disclose or use except as authorized in writing by the study sponsor

- Related or possibly related to participation in the research (i.e., possibly related means there is a reasonable possibility that the incident experience, or outcome may have been caused by the procedures involved in the research)
- Suggests that the research places subjects or others at greater risk of harm (including physical, psychological, economic, or social harm).

Adverse Event

An **adverse event** (AE) is any symptom, sign, illness or experience that develops or worsens in severity during the course of the study. Intercurrent illnesses or injuries should be regarded as adverse events. Abnormal results of diagnostic procedures are considered to be adverse events if the abnormality:

- results in study withdrawal
- is associated with a serious adverse event
- is associated with clinical signs or symptoms
- leads to additional treatment or to further diagnostic tests
- is considered by the investigator to be of clinical significance

Serious Adverse Event

Adverse events are classified as serious or non-serious. A **serious adverse event** is any AE that is:

- fatal
- life-threatening
- requires or prolongs hospital stay
- results in persistent or significant disability or incapacity
- a congenital anomaly or birth defect
- an important medical event

All adverse events that do not meet any of the criteria for serious should be regarded as **non-serious adverse events**.

8.1.1 Investigator reporting: notifying the IRB

Federal regulations require timely reporting by investigators to their local IRB of unanticipated problems posing risks to subjects or others. The following describes the NYULMC IRB reporting requirements, though Investigators at participating sites are responsible for meeting the specific requirements of their IRB of record.

Report Promptly, but no later than 5 working days:

Researchers are required to submit reports of the following problems promptly but no later than 5 working days from the time the investigator becomes aware of the event:

- **Unanticipated problems including adverse events that are unexpected and related**
 - **Unexpected:** An event is “unexpected” when its specificity and severity are not accurately reflected in the protocol-related documents, such as the IRB-approved research protocol, any applicable investigator brochure, and the current IRB-approved informed consent document and other relevant sources of information, such as product labeling and package inserts.
 - **Related to the research procedures:** An event is related to the research procedures if in the opinion of the principal investigator or sponsor, the event was more likely than not to be caused by the research procedures.
 - **Harmful:** either caused harm to subjects or others, or placed them at increased risk

Other Reportable events:

The following events also require prompt reporting to the IRB, though **no later than 5 working days**:

- **Complaint of a research subject** when the complaint indicates unexpected risks or the complaint cannot be resolved by the research team.

CONFIDENTIAL

- **Protocol deviations or violations** (includes intentional and accidental/unintentional deviations from the IRB approved protocol) for any of the following situations:
 - *one or more participants were placed at increased risk of harm*
 - *the event has the potential to occur again*
 - *the deviation was necessary to protect a subject from immediate harm*
- **Breach of confidentiality**
- **Incarceration of a participant** when the research was not previously approved under Subpart C and the investigator believes it is in the best interest of the subject to remain on the study.
- **New Information indicating a change to the risks or potential benefits** of the research, in terms of severity or frequency. (e.g. analysis indicates lower-than-expected response rate or a more severe or frequent side effect; Other research finds arm of study has no therapeutic value; FDA labeling change or withdrawal from market)

Reporting Process

The reportable events noted above will be reported to the IRB using a Reportable New Information submission and will include a description of the event with information regarding its fulfillment of the above criteria, follow-up/resolution, and need for revision to consent form and/or other study documentation. Copies of each report and documentation of IRB notification and receipt will be kept in the Clinical Investigator's study file.

9 Statistical Considerations

9.1 Study Hypotheses

Patient in clinics receiving the EHR-based alerts will have higher rates of adherence to guideline recommended medical therapy.

Providers will like the EHR-based alerts and will want to continue to use them in their practice.

9.2 Sample Size Determination

In order to have 80% power to detect a 10% improvement in prescribing for each intervention arm vs. control, we will require a total of at least 1503 patients (501 per arm). Based on prior data, we estimate that alerts will trigger for a sample between 1500-2000 patients, but are unable to accurately control the specific number of patients due to fluctuating clinical volume at practices.

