4.4 Vulnerable Subjects

No vulnerable patients will be enrolled.

For the survey, we will recruit NYULH cardiologists who received the BPAs or messages. The only way to obtain feedback on the BPAs and electronic messages is from the cardiologists at NYULH who received the BPAs and electronic messages, as they are the only ones who can comment on the acceptability, usefulness, and ease of use of these EHR tools. Cardiologists will be informed that their decision to participate or not, and their responses, will in no way affect their employment, salary, or performance evaluations and they will be reminded that they can stop participating whenever they want. Their information will be de-identified and completely anonymous. No identifiable PII or health information will be collected.

5 Strategies for Recruitment

Eligible patients from the chosen practice sites will be identified electronically within EPIC using an algorithm developed by the study team and NYULH's DataCore. This algorithm reviews patient records for $EF \leq 40\%$ on most recent echocardiogram, and exclusion criteria listed above. Patients meeting eligibility will be automatically included, and all data collection will take place passively via the NYULH EHR system, EPIC. An EPIC reporting analyst will extract the relevant parameters from EPIC into a report. Patients from the selected practice sites will undergo their usual interactions with their providers and no study-specific activities will take place.

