5.2 Participant Withdrawal or Termination

Not applicable as the subjects are recruited at the clinic level.

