5.3 Provider Survey Recruitment

For the provider survey, we will recruit cardiologists who received the BPA or electronic message through emails (see attachment). They will be made aware that completing the survey is completely anonymous and will in no way impact their employment. The recruitment emails will be sent via listservs of cardiologist who received the BPAs and electronic messages. These listservs are specific for those cardiologists who received BPAs or electronic messages and the survey does not require cardiologists to self-select whether they received a BPA or a message. Only cardiologists who received a BPA or electronic message will be contacted. We will send an initial recruitment email and a subsequent follow up email.

The consent form will be attached to the email. It will also be available via link within the first question in Qaltrix. The first question in Qaltrix asks the provider to review the consent document and requires the provider to click a button stating that they are consenting to participate before being shown the remaining survey questions. If the provider does not click this button, they will not be able to move forward or complete the survey.

6 Study Schedule

Participants will be included in this study by virtue of meeting eligibility criteria and having a patient encounter during the study period. There are no study-specific visits. Any patient meeting criteria who has one or more patient encounters during the study period will be included. Therefore, no study-specific visits are relevant for this study, so there is no schedule of visits.

CONFIDENTIAL

This material is the property of the NYU School of Medicine and Langone Health. Do not disclose or use except as authorized in writing by the study sponsor

7 Study Procedures / Evaluations

There are no study-specific procedures that patients will undergo. They will receive care as usual by their outpatient providers. The EHR algorithm developed by the study team identifies eligible patients with EF \leq 40% on most recent echocardiogram, and exclusion criteria listed above. The EHR algorithm will also capture information on demographics, diagnoses in the patient's problem list, prescription history, allergies, EF, and relevant lab results.

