For patients meeting the eligibility criteria, a message in the EHR will automatically be sent to the provider. The provider will receive either a Best Practice Alert (BPA) or electronic message indicating that their heart failure patient is not on guideline-recommended therapy. The message will offer guidance for physician decision-making regarding HFrEF care. The study team presented the proposed project to the NYULH MCIT Project Portfolio Review Committee on February 11, 2021 and was approved to work with MCIT to build the electronic messages. Providers will be notified through the Weekly Epic Update and in presentations to medical directors that they may see the alert prior to the start of the study.

Patients' clinical outcomes will be monitored through EHR data collection for 18 months. Data collection will include elements of protected health information including patient name, medical record number, address zip code, and service dates. These will be necessary for data linkages and in order to track patients for receipt of intervention and clinical outcomes. All PHI data will be kept on a secure NYULH server and destroyed at the earliest possible point. Data on the patient's medication prescription, hospitalization, hospitalization for HF, and mortality will be recorded as study outcomes. The study team members will not collect this information directly; data will be collected in NYULH's EHR system, EPIC, and an EPIC Reporting analyst from DataCore will extract the relevant parameters from the EHR into a report.

Data points that will be collected for research purposes
Medication prescription
Hospitalization
Hospitalization for HF
Mortality
Name
Medical record number
Address zip code
Service dates

Provider survey data will be anonymously collected via Qualtrix. No identifiable information, PII, or health information will be collected. The URLs for the survey are below:

BPA version = https://nyumc.yul1.qualtrics.com/jfe/preview/previewId/f42fb1cb-b997-4fb8-8f60-9e311e6b6320/SV_7P3UhfVSH6KgpuK?Q_CHL=preview&Q_SurveyVersionID=current

IBM version = https://nyumc.yul1.qualtrics.com/jfe/preview/previewId/c97ab951-3feb-478a-8af8-a53e9abbe02d/SV_7PQoQunPLM8I8ZU?Q_CHL=preview&Q_SurveyVersionID=current

8 Safety and Adverse Events

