11.3 Informed Consent Process

We will obtain a waiver of informed consent and a waiver of HIPAA authorization for patients seen in the participating clinics to acknowledge their participation at a clinic level. The risks to subjects are exactly equivalent to the risks experienced in the standard setting of patient care. The new module to be activated in EPIC relates only to guidance for physician decision-making regarding HFREF care, and has no impact on disclosure or treatment of PHI. Patients will receive care from their providers in the usual way. The only difference is the interface with the electronic health record that is used by the physician during the course of the patient encounter. The autonomy of the provider to make decisions about patient care will not be affected. It is impracticable to obtain consent from patients for receipt of standard medical care by their usual providers. It is unclear what they would be providing consent for, since they will receive care as usual from their providers. Patients will not be provided with additional information. They will be treated as usual by their providers and the providers' experience with the module is irrelevant to their patient experience.

For provider surveys, we are requesting a waiver of documentation of consent. These surveys present no more than minimal risk to providers. Prior to beginning survey questions, providers will be given consent form that contains all pertinent study and contact information. The consent form will be attached to the recruitment email and also will be available via link in Qaltrix prior to the survey. The providers will be asked to acknowledge consent through clicking a button within Qaltrix before they are able to participate in the survey questions. Providers will be informed that they may agree not to participate and that this will have no bearing on their employment status.

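### Section 9.2 ties its 80% power to no clustering allowance, although alerts reach patients through clinics or providers; adding pre-study cluster prescribing rates to 9.3 would recover power cheaply

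*Combined protocol and SAP*

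**What the plan says.** Section 9.2 (Sample Size Determination) gives 80% power, a 10% improvement, comparisons of each intervention arm with control, and the statement "we will require a total of at least 1503 patients (501 per arm"). It expects alerts to trigger for 1500–2000 patients and adds that the investigators "are unable to accurately control the specific number of patients due to fluctuating clinical volume at practices". It gives no significance level, control rate, absolute or relative scale, ICC, design effect or number of clusters.

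Other sections place the intervention above the patient:

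- **Clinic.** The hypothesis in 9.1 reads "Patient in clinics receiving the EHR-based alerts will have higher rates of adherence". Section 5.2 says "subjects are recruited at the clinic level". Section 11.3 seeks the waiver for "patients seen in the participating clinics to acknowledge their participation at a clinic level". Section 5 says "Eligible patients from the chosen practice sites will be identified electronically within EPIC".
- **Provider.** Section 7 says "The provider will receive either a Best Practice Alert (BPA) or electronic message". Section 5.3 says of the survey mailing lists: "These listservs are specific for those cardiologists who received BPAs or electronic messages".

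The readable text does not name the unit of allocation. The Protocol Summary puts the health system at about 60 outpatient cardiology practices. Section 9.3 names McNemar's tests and adjustment for patient and provider characteristics. It names no term for clustering and no pre-study prescribing rate.

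**The concern.** Patients of one clinic or cardiologist share both the alert type and the prescriber's habits, so their outcomes are correlated. A patient count then overstates the information available. Power depends largely on the number of clusters, the ICC and how much between-cluster variation the analysis removes. Section 9.2 addresses none of these, and 80% power is the only operating characteristic the plan states.

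The team cannot control patient numbers, and adding patients within a fixed set of clinics helps little. The planners therefore cannot tell in advance whether 1500–2000 patients deliver the stated power. The main lever left to them is the analysis, and 9.3 leaves out the covariate most directly aimed at between-cluster variation.

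**Working it through.** **Inputs from the plan:** 80% power; 10% improvement; 501 per arm (3 × 501 = 1503); about 60 practices.

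**Assumptions not in the plan:** absolute 10 points; two-sided 0.05 per comparison; unpaired two-proportion test; equal clusters; control rates of 45%, 35%, 20% and 10%; ICC of 0.05 as an illustration; all 60 practices used, 20 per arm, so m = 501/20 = 25.05 patients per clinic.

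**Step 1: can 501 be reproduced?** With control rate p1, p2 = p1 + 0.10 and p̄ their mean, the requirement per arm is

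n = [1.96·√(2p̄(1−p̄)) + 0.8416·√(p1(1−p1) + p2(1−p2))]² / 0.10².

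The maximum is at 45% against 55%: n = 391.3, so 392 (412 with continuity correction). No control rate gives 501 on these terms. Added assumptions do reach about 501, for example 35% against 45% at alpha 0.05/3 (501.2), a design effect of about 1.28 on 392, or 25% dropout at a 35% control rate. The source of 501 cannot be identified.

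**Step 2: how much clustering does 501 tolerate?** The design effect is DE = 1 + (m − 1)·ICC. Power stays at 80% while DE ≤ 501/n, so the break-even ICC is (501/n − 1)/24.05. At ICC 0.05, DE = 1 + 24.05 × 0.05 = 2.20 and the effective size is 501/2.20 = 227 per arm.

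| Control rate | n, no clustering | Power at 501, no clustering | 501/n | Break-even ICC | Power at ICC 0.05 |
|---|---|---|---|---|---|
| 45% | 391.3 | 88.7% | 1.28 | 0.012 | 57% |
| 35% | 375.6 | 89.9% | 1.33 | 0.014 | 59% |
| 20% | 293.2 | 95.6% | 1.71 | 0.029 | 69% |
| 10% | 199.0 | 99.4% | 2.52 | 0.063 | 85% |

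**Step 3: other cluster structures at ICC 0.05.**

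- 15 clinics per arm (m = 33.4, DE 2.62): 50%, 51%, 62%, 78%, in the same order of control rates.
- 10 clinics per arm (m = 50.1, DE 3.46): 40%, 41%, 50%, 67%.
- Provider clusters of 5 or 10 patients (DE 1.20, 1.45), with no further clinic-level correlation: 84% or 77% at a 35% control rate, 92% or 86% at 20%.

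**Step 4: do more patients help?** With 20 clinics per arm, a 35% control rate and ICC 0.05, the difference detectable at 80% power falls only from 12.9 points (501 per arm) to 12.2 points (667 per arm, or 2000/3).

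**Step 5: what does a pre-study cluster rate add?** A clinic's rate from L look-back patients has reliability R = L·ICC/(1 + (L − 1)·ICC). At ICC 0.05 this is 0.57, 0.72 and 0.84 for L = 25, 50 and 100. If the true clinic rates before and during the study correlate at s, the covariate's correlation with the clinic effect is r = s·√R. The design effect becomes DE = (1 − ICC) + m·ICC·(1 − r²). For s = 0.8 and L = 100, r² = 0.64 × 0.84 = 0.538 and DE = 0.95 + 25.05 × 0.05 × 0.462 = 1.53.

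Power with 20 clinics per arm and ICC 0.05, over L = 25 to 100:

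| Control rate | No covariate | s = 0.6 | s = 0.8 |
|---|---|---|---|
| 35% | 59% | 64–67% | 69–74% |
| 20% | 69% | 75–77% | 79–84% |
| 10% | 85% | 89–91% | 92–95% |

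These use a normal reference. At ICC 0.05 a t reference with 38 degrees of freedom (20 clinics per arm) lowers power by about 2 points.

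**The case against.** The strongest objection is that nothing here is a demonstrated error. On the most natural reading 501 exceeds the unclustered requirement by at least 28%, and it may already include an allowance that the authors did not write down. That stands. A reader might infer that 501 is a miscalculation or that the trial is underpowered. The documents support neither, because the ICC, control rate and clinic count above are all assumed.

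The control rate also matters. Alerts trigger only for patients not on recommended therapy. If the outcome is starting a missing drug, a low control rate is the more natural one, and at 10% power is still 85% at ICC 0.05 and 97.9% at ICC 0.01. That is fair, and it is why results are shown across control rates. The covariate raises power at each rate tabulated.

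The study schematic is not shown in the text reviewed and may give the unit of allocation and the clusters per arm. The point therefore does not rest on their absence; it rests on 9.2 making no use of them.

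Finally, 9.3 names McNemar's test and provider-level adjustment. A paired comparison or those covariates could remove some between-cluster variance, so the simple design effect may not describe the planned analysis exactly. That limits the precision of the figures. It does not connect the 80% to any stated calculation, and the listed covariates do not include a cluster's own past prescribing. The size of the covariate gain is uncertain, since it depends on how stable cluster rates are over time.

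**Conclusion.** The point holds as a conditional one. The stated 80% cannot be tied to a comparison in which patients are grouped by clinic or provider, and a cheap improvement to the analysis is available. With 20 equal clinics per arm, an absolute 10 points and two-sided 0.05, the claim survives up to an ICC between 0.012 (45% control rate) and 0.063 (10%). At ICC 0.05, power runs from 57% to 85%. Fewer clinics lower these figures; small provider clusters with no clinic-level correlation raise them. No shortfall is demonstrated. The firmer part is the covariate: for no extra enrolment it adds roughly 5 to 16 points of power at control rates of 35% and 20%, and 4 to 10 points at 10%, if ICC is 0.05 and stability lies between 0.6 and 0.8.

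**What to change.** 1. **Section 9.3.** Fit a cluster-adjusted model. Add to its covariates each allocation unit's pre-study prescribing rate among patients who would have met the alert criteria. Take the rate from an Epic look-back long enough to make it reliable; section 7 says the algorithm already captures prescription history.
2. **Section 9.2.** Make the 80% conditional. Give the power, or the difference detectable at 80%, for 1500–2000 patients under the actual unit of allocation and the test actually used, over a stated ICC range (for example 0.01–0.10). The prior data behind the volume estimate may allow the ICC to be estimated. State the significance level per comparison, the control rate and whether the 10% is absolute, and say whether 501 already includes a clustering or multiplicity allowance.

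The cost is one extra Epic extract, one recalculation and rewording of two short sections. The stated power may come out less favourable, and the covariate gains little if cluster rates are unstable over time.

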9.3 Statistical Methods

We will begin all analyses with descriptive summary statistics and graphical displays of all variables. Primary analyses will utilize McNemar's tests for medication prescriptions and patient outcomes of hospitalization and mortality. We will adjust for patient demographics and clinical characteristics, as well as provider-level characteristics, such as demographics, panel size, insurance mix, and sub-specialty training.

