Title	BETTER CARE – HF: Building Electronic Tools To Enhance and Reinforce Cardiovascular Recommendations – Heart Failure
Short Title	BETTER CARE – HF: Building Electronic Tools To Enhance and Reinforce Cardiovascular Recommendations – Heart Failure
Brief Summary	This study will test two types of electronic health record (EHR)-based alerts to improve guideline-adherent care for patients with heart failure and reduced ejection fraction (HFrEF). Alerts will be triggered for patients with ejection fraction (EF) \leq 40% who are not on guideline-recommended medical therapy. The two types of alerts tested will be a Best Practice Alert (BPA) and an electronic message.
Objectives	To test two types of EHR-based alerts that promote appropriate medical therapy for patients with HFrEF.
Methodology	Prospective cohort study
Endpoints	Primary endpoint: medication prescribing patterns Secondary endpoint: hospitalization and mortality
Study Duration	Eighteen months
Participant Duration	Eighteen months
Population	Patients with EF \leq 40%
Study Sites	One single health system, NYULH, consists of approximately 60 outpatient cardiology practices.
Number of participants	Up to 2000 participants
Statistical Analysis	We will begin all analyses with descriptive summary statistics and graphical displays of all variables. Primary analyses will utilize McNemar's tests for medication prescriptions and patient outcomes of hospitalization and mortality. We will adjust for patient demographics and clinical characteristics, as well as provider-level characteristics, such as demographics, panel size, insurance mix, and sub-specialty training.

CONFIDENTIAL

This material is the property of the NYU School of Medicine and Langone Medical Center. Do not disclose or use except as authorized in writing by the study sponsor

Schematic of Study Design

CONFIDENTIAL

This material is the property of the NYU School of Medicine and Langone Health. Do not disclose or use except as authorized in writing by the study sponsor

1 Introduction, Background Information and Scientific Rationale

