3.3 Study Endpoints

Outcomes measured at the prescription encounter level include whether there is a prescription for BB, ACE-I/ARB/ARNI, and/or MRA. Secondary patient outcomes include hospitalization, hospitalization for HF, and mortality.

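### McNemar's paired test is named as primary, but Section 9.2 powers each alert arm against control; the readable text defines no pair and names no model for the promised adjustment

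*Combined protocol and SAP*

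**What the plan says.** Section 9.3, repeated in the Protocol Summary, gives the whole primary analysis in two sentences. The first is "Primary analyses will utilize McNemar's tests for medication prescriptions and patient outcomes of hospitalization and mortality". The second begins "We will adjust for patient demographics and clinical characteristics, as well as provider-level characteristics" and names no model.

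Section 9.2 asks for "80% power to detect a 10% improvement in prescribing for each intervention arm vs. control", with 501 patients per arm and 1,503 in total. It expects 1,500 to 2,000 patients but says that the investigators "are unable to accurately control the specific number of patients due to fluctuating clinical volume at practices".

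Section 9.1 hypothesises: "Patient in clinics receiving the EHR-based alerts will have higher rates of adherence to guideline recommended medical therapy". This implies a comparison of clinics, but names neither a control nor separate alert arms.

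On units, Section 3.3 says "Outcomes measured at the prescription encounter level include whether there is a prescription for BB, ACE-I/ARB/ARNI, and/or MRA", Section 6 admits patients with one or more encounters, and Section 5.2 says that recruitment is at clinic level. Section 7 describes only the alerted side: "For patients meeting the eligibility criteria, a message in the EHR will automatically be sent to the provider". The Protocol Summary calls the design a prospective cohort study.

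**The concern.** McNemar's test uses only discordant pairs: the same patient at two times, or two matched patients. Section 9.2 asks a question about separate groups. The readable text gives no rule for forming a pair, and with encounter-level outcomes even the thing to be paired (patient or encounter) is open. The test takes no covariates, so the adjustment sentence cannot be carried out with it. A regression may be intended, but none is named.

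Two analysts could follow Section 9.3 faithfully and report different primary results, one of them without the control arm. Since this is the primary analysis and the document has no fuller analysis section, the choice would be made after outcomes are available.

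**Working it through.** **1. Does 501 per arm reveal the intended test?** 3 × 501 = 1,503 agrees. The 501 itself can be neither confirmed nor refuted, because alpha and the control rate are not given.
- Unpaired, 10 points absolute, two-sided 0.05, 80% power: at most 392 per arm at any control rate (412 with continuity correction). 501 is reached under other assumptions, for example exactly at two-sided 0.0167 with a control rate of about 35%.
- McNemar, pairs = (z_α√π + z_β√(π − d²))²/d², with d = 0.10 and π the discordant proportion: at two-sided 0.05, 501 pairs need π of about 63–66%. If pair members are independent, π is at most 0.45 × 0.45 + 0.55 × 0.55 = 50.5%, which gives about 395 pairs.

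So 501 does not point to a paired calculation, though it does not rule one out.

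**2. Before/after reading.** The control arm does not enter. For a drug class that is missing at the alert, and if only starts are counted, every change goes one way and the exact test is a sign test. Five changes give 2 × 0.5⁵ = 0.0625; six give 2 × 0.5⁶ = 0.031. The chance of p<0.05 with no alert effect is therefore P(X ≥ 6), with X binomial. Uptake rates are assumptions.

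| Patients off the class | 1% background uptake | 2% background uptake |
|---|---|---|
| 501 | 39% | 94% |
| 250 | 4% | 38% |

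For mortality there is no meaningful before value: everyone starts alive.

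**3. Between-arm reading.** Patients were paired at random 10,000 times, using McNemar's chi-square without continuity correction. The counts are illustrations.

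| Control vs alert | Unpaired result | Across random pairings |
|---|---|---|
| 175/501 vs 206/501 | 6.19 points, p=0.044 | 6.19 points always; p about 0.028 to 0.062; 11% not significant |
| 175/501 vs 225/501 | 50/501 = 9.98 points | difference unchanged; all significant |
| 227/650 vs 206/501 | 6.19 points, p=0.031 | middle 95%: 4.2 to 8.2 points, p 0.007 to 0.17; 44% not significant |

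In the last row 650 − 501 = 149 controls are dropped. With a third arm of 501 the total is 1,652, inside the range that Section 9.2 expects.

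**4. Power once clustering is allowed for.** Assumed: 30% vs 40%, two-sided 0.05, 501 per arm. With k clinics per arm, mean size m = 501/k and cluster-size coefficient of variation CV, the design effect is DE = 1 + ((1 + CV²)m − 1) × ICC. Power = Φ(0.10/√(0.45 × DE/501) − 1.96), where 0.45 = 0.3 × 0.7 + 0.4 × 0.6. About 60 practices over three arms gives k = 20 if all take part in equal shares. ICC and CV are assumptions. At ICC 0 the power is 92%.

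| Layout per arm | ICC 0.01 | ICC 0.02 | ICC 0.05 |
|---|---|---|---|
| 20 equal clinics | 85% | 78% | 61% |
| 20 clinics, CV 0.7 | 82% | 72% | 51% |
| 10 equal clinics | 78% | 66% | 43% |

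For example, 20 equal clinics at ICC 0.02: DE = 1 + (25.05 − 1) × 0.02 = 1.481, power 78%.

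**The case against.** The strongest reply is that the schematic of the study design is not shown and might depict matching or a before/after comparison. That stands as a limit: what is established is a test that cannot be reconciled with the readable plan, not proof that no pairing was ever intended. But the statistical section would still have to state the pair in words, and a pair would not supply the missing adjustment model.

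It is also fair that the figures rest on readings the plan does not state. Random pairing is proposed nowhere. The equal-arm example was chosen close to p=0.05. The before/after rates assume that every patient lacks the class and none stops it, whereas Section 3.3 covers three classes and Section 4.2 does not require patients to be untreated. They show what the wording permits, not what the trial would report.

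A reader might infer that, with equal arms, the between-arm estimate is sound. The documents do not support that: the design is labelled a prospective cohort and the readable text describes no randomization. Equal arms mean only that pairing leaves the difference unchanged; confounding is a separate matter. Nor does Section 9.1 itself set each alert arm against control; only Section 9.2 does.

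Ignoring clustering is not peculiar to McNemar's test. Any unclustered test would do the same.

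**Conclusion.** Wrong as written. The named primary test needs pairs that the readable text never defines, does not match the comparison for which the study is sized, and cannot carry the promised adjustment.

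The consequence depends on the reading. Before/after is the serious one, because control is lost and ordinary prescribing can produce significance on its own; how often depends on the assumed uptake and on how many patients are off the class. Between equal arms the effect is small and confined to results near the threshold. Between unequal arms paired one to one, both the estimate and the p-value move.

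It would go too far to conclude that the trial will report a false result or that its arm comparison is invalid. The documents show only that the primary analysis is not determined by its own text.

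**What to change.** In Section 9.3 and the Protocol Summary, replace the McNemar and adjustment sentences with the following.

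- **Analysis.** Compare each alert arm with control, allowing for clustering at the unit at which alerts are assigned. Section 9.1 suggests the clinic and Section 7 the provider, so state which. Carry the listed patient and provider covariates. One option is a mixed-effects logistic model with arm as fixed effect, a random intercept for that unit, small-sample degrees of freedom, and standardised risk differences with 95% confidence intervals. Keep the covariate set small for death if events are few.
- **Prescribing outcome.** Say which drug class or classes form the primary outcome, with MRA-ineligible patients left out of the MRA outcome. Use either one value per patient over a fixed window or an encounter-level model that also clusters by patient, and align Section 3.3. Fix the window before outcome data are seen.
- **Hospitalization and death.** Give both a common fixed follow-up window, or use a time-to-event model with clustering. Entry is by encounter, so later entrants may have shorter follow-up.
- **If a pairing was intended,** define it and show how control enters.
- **Section 9.2.** Recheck the power and restate it with alpha, control rate, ICC, and the number and size of clusters.

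The cost is wording, standard software, and arm and cluster identifiers. The statistical price is wider intervals, which come from allowing for clustering rather than from dropping McNemar's test; the size is in the power table above. The remedy for lower power is to restate the figure, not to enrol more: with 20 equal clinics per arm, solving n = 353.2 × (1 + (n/20 − 1) × 0.05) for 80% power at ICC 0.05 gives about 2,870 per arm, far beyond the expected 1,500 to 2,000 in total.
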